7.2 Reporting of Adverse Events

7.2.1 Adverse Events

Refer to Section 6.2.1 for a summary of ongoing safety review during the study, including review of any new Suspected Unexpected Serious Adverse Reactions (SUSARs).

Serious AEs (SAEs) will be collected from the time the patient signs the informed consent form until 28 days after the last dose of study drug, or until the initiation of an investigational agent or cytotoxic chemotherapy, whichever comes first, and as per Section 7.2.3. Serious AEs will be collected on the Adverse Event eCRF from the time of first dose of study drug until 28 days after the last dose of study drug, or until the initiation of an investigational agent or cytotoxic chemotherapy, whichever comes first.

Adverse Events of Special Interest (AESI), as defined in Section 7.2.4, should be collected on the AESI Form from the time of first dose of study drug until 28 days after the last dose of study drug and reported to Forma Therapeutics Pharmacovigilance within 24 hours of knowledge of event.

Non-serious adverse events will be collected and reported on the Adverse Event eCRF from the time of the first dose of study drug until 28 days after the last dose of study drug, or until the initiation of an investigational agent or cytotoxic chemotherapy, whichever comes first.

Patients withdrawn from the study because of AEs will be followed by the Investigator until the outcome is determined. When appropriate, additional written reports and documentation will be provided.

All AEs beginning after the last exposure of study drug must be reported to the Sponsor or its designee if the onset of the AE was within 28 days of the last exposure to study drug. All AEs, whether serious or nonserious, that are judged by the Investigator to be at least possibly related to study drug administration must be reported to the Sponsor or its designee regardless of how much time has elapsed since the last exposure to study drug (i.e., beyond 28 days of the last exposure to study drug).

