7.2.2 Laboratory Abnormalities

To the extent possible, all new or worsening laboratory abnormalities observed during the course of the study will be included under a reported AE describing a clinical syndrome (e.g., elevated blood urea nitrogen and creatinine in the setting of an AE of "renal failure" or elevated ALT/AST in the setting of an AE of "hepatitis"). In these cases (e.g., an AE of renal failure), the laboratory abnormality itself (e.g., elevated creatinine) does not need to be recorded as an AE.

An abnormal laboratory value that is not already associated with an AE (e.g., symptoms or diagnosis) is to be recorded as an AE only if an action on the study drug or concomitant medication is made as a result of the abnormality, if intervention or management of the abnormality is required, or at the discretion of the Investigator.

Patients experiencing laboratory abnormalities will be assessed and appropriate evaluations performed until all parameters have returned to baseline levels, or are consistent with the patient's then-current physical condition.

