7.2.4 Adverse Events of Special Interest

As described in Section 5.5.3, adverse events potentially associated with liver injury have been identified as AESI. These AESI (regardless if serious or non-serious) include the following:

- a. All events of Grade 2 or higher elevations in ALT, AST, or total bilirubin in patients with normal LFTs at baseline; in patients with elevated LFTs at baseline, one Grade shift or higher in ALT, AST, or total bilirubin;
- b. Any hepatic adverse event, e.g., acute hepatitis, cholestatic hepatitis, cholestasis, or hepatic insufficiency

AESI occurring from time of first dose through 28 days after last dose must be reported as outlined below:

- a. Report to Forma Therapeutics Pharmacovigilance within 24 hours of knowledge of event
- b. If the event meets both AESI and SAE criteria, complete both the SAE and AESI form
- c. If the event is non-serious, complete the AESI form alone

Relevant forms (AESI, SAE, or both) should be submitted via fax ([contact]) or email ([contact]) to Forma Therapeutics Pharmacovigilance.

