Treatment-related TEAEs leading to death	Х			
TEAE of Special Interest	X			

All AEs occurring on study (treatment emergent or not) will be provided in patient data listings. The following additional by-patient listings of AEs (treatment emergent or not) will be provided: all SAEs, all AEs leading to withdrawal of study drug, all AEs leading to dose modification, and all AEs leading to death.

In addition, a listing of all deaths with related information regarding the death will be provided, including AEs leading to death, as well as deaths that are not reported as due to an adverse event.

A summary of DLTs by system organ class and preferred term, and a listing of all AEs that caused a DLT, will be provided for the DLT evaluable set.

Adverse Events of Special Interest (AESI): Hepatotoxic and Gallbladder disorder

Some patients taking FT-2102 have experienced transaminase elevations. As such, summary tables of AEs for hepatotoxicand gallbladder disorders will be created, with tabulations of the number of patients experiencing such events by SOC and PT. Under each PT within each grouping, the time to onset will be summarized descriptively, and time to resolution will be summarized using Kaplan-Meier (KM) methods.

In addition, overall summary table for TEAEs for each AESI group will be created. It will include the number of patients with TEAEs, treatment-related TEAEs, grade 3 or 4 TEAEs, treatment related grade 3 or 4 TEAEs, serious TEAEs, treatment related serious, TEAEs resulting in FT-2102 discontinuation, treatment related TEAEs resulting in FT-2102 discontinuation; TEAEs leading to dose reduction, TEAEs leading to dose hold, treatment related TEAEs resulting in on-treatment death, treatment related TEAEs resulting in death.

All TEAEs in each group occurring on study will be provided in corresponding patient data listings.

The table below presents preferred terms in each subgroup:

Hepatotoxicity Grouping	Gallbladder disorder Grouping
Alanine aminotransferase increased	Biliary tract disorder
Aspartate aminotransferase increased	Biliary colic
Hypertransaminasemia	
Liver function test abnormal	Cholangitis
Liver function test increased	Cholestasis
Transaminases increased	
Blood alkaline phosphatase increased	
Hyperbilirubinemia	
Blood bilirubin increased	

AESI: Differentiation Syndrome

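### The SAP does not tabulate the hepatic AESI as protocol 7.2.4 defines it: its AESI tables rest on AE preferred terms, so some laboratory-defined cases can be missing

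*SAP*

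**What the plan says.** Protocol 7.2.4 gives the hepatic AESI two limbs. Limb (a) is a laboratory definition. It covers "All events of Grade 2 or higher elevations in ALT, AST, or total bilirubin in patients with normal LFTs at baseline" and, "in patients with elevated LFTs at baseline, one Grade shift or higher in ALT, AST, or total bilirubin". Limb (b) covers reported events: "Any hepatic adverse event, e.g., acute hepatitis, cholestatic hepatitis, cholestasis, or hepatic insufficiency".

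On collection, protocol 7.2.1 says AESI "should be collected on the AESI Form from the time of first dose of study drug until 28 days after the last dose". Section 7.2.4 adds: "If the event is non-serious, complete the AESI form alone". Section 7.2.2 governs laboratory values not already tied to an AE. Such a value "is to be recorded as an AE only if an action on the study drug or concomitant medication is made", or if it needs intervention or management, or if the investigator decides to record it.

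SAP VIII.B plans hepatotoxicity and gallbladder tables "with tabulations of the number of patients experiencing such events by SOC and PT". Each group is a list of preferred terms. Time to onset and time to resolution are given under each preferred term, and an overall table for each group counts patients with related, severe, serious and dose-changing events. No laboratory criterion is stated, and the SAP does not name the AESI Form as a source.

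SAP VIII.C separately plans CTCAE shift tables for ALT, AST, alkaline phosphatase and bilirubin, eDISH plots, and counts of patients exceeding multiples of the ULN.

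**The concern.** Liver injury is the only AESI that the protocol names. A reader of the study report will take the table labelled hepatic AESI as the incidence of the protocol's AESI, but the two rest on different definitions and different data sources. A patient with normal baseline tests and a Grade 2 elevation that no one acts on or records as an AE meets 7.2.4(a) and appears in no AESI table. In protocol Table 7 the hold triggered by grade alone starts at Grade 3, so Grade 2 values without a drug action are foreseeable. At stake are the hepatic AESI incidence and its timing. The primary efficacy endpoint is not affected.

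**Working it through.** The plan states no figure to reproduce. The check sets the sections side by side.

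1. **Definition.** Protocol 7.2.4(a) uses three parameters, CTCAE grade and baseline status. The elevated-baseline part can apply in practice, because inclusion criterion 7 admits bilirubin up to 2 times ULN (3 times in Gilbert syndrome) and AST or ALT up to 3 times ULN.

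2. **Route into the AE data.** Section 7.2.2 opens three routes for an isolated elevation: a change to study drug or concomitant medication, a need for intervention or management, or investigator discretion. Grade alone is not a route. Two sites with the same Grade 2 value can therefore record it differently.

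3. **Route into the AESI tables.** SAP VIII.B starts from AE preferred terms. An elevation that takes none of the three routes cannot reach the tables, even if an AESI Form was filed.

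4. **What SAP VIII.C recovers.** The shift tables compare baseline grade with worst grade and include unscheduled visits. If baseline is judged parameter by parameter, the cells show how many patients meet 7.2.4(a) on ALT, on AST and on total bilirubin, each taken alone.

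5. **What SAP VIII.C does not recover.** Let a, b and c be the patients who meet the definition on ALT, AST and total bilirubin, out of n. The number who meet it on at least one parameter satisfies max(a, b, c) ≤ N ≤ min(n, a + b + c). Separate tables fix only these bounds. The ULN flags do pool AST with ALT in one row, but they use multiples of ULN on post-baseline values with no comparison to baseline, and total bilirubin alone is a separate row. The shifts to each planned visit describe the cohort at that visit. They are not a patient's time to onset or resolution.

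6. **Precedent in the same SAP section.** The differentiation syndrome AESI combines AE terms with leukocyte counts, creatinine and vital signs. The hepatic AESI has no such laboratory component.

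7. **Scale.** The documents give no rate of Grade 2 elevations left off the AE page. For Cohort 1, with about 190 patients planned, each percentage point missed is 190 × 0.01 = 1.9 patients.

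**The case against.** The strongest reply is that the liver data are already well covered and that nothing promised is missing. Protocol 9.2.4.2 promises an assessment of changes in liver function tests, and SAP VIII.C delivers one. Section 7.2.4 is chiefly an expedited reporting rule, and the SAP tables are openly lists of preferred terms. Section 5.5.3 also calls for testing, medication review and closer monitoring when there is evidence of new liver injury. That may count as management under 7.2.2 and so bring Grade 2 values onto the AE page. Most of this stands. It limits the size of the problem but does not supply the protocol-defined count.

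Four stronger readings are tempting, and the documents do not support them.

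- A reader might infer that these elevations are never counted. The SAP VIII.C shift tables count them by parameter and do use baseline grade.
- A reader might infer that a non-serious laboratory AESI goes only to pharmacovigilance. In context, the instruction to use the AESI form alone contrasts with the SAE form. Section 7.2.1 still sends non-serious AEs to the AE eCRF, and the protocol does not say whether a laboratory-only AESI must also be entered there.
- A reader might infer that the AESI table always understates. The omission is downward, but the term list has no grade floor and includes alkaline phosphatase increased and biliary colic, which lie outside 7.2.4(a). The net difference could go either way, and a recorded Grade 1 AE would date onset earlier.
- A reader might add 5% to 15% of patients to the roughly 20% with hepatic events in section 5.5.3 and report 25% to 35%. The 5% to 15% has no source in the documents. The 20% covers all patients treated with FT-2102 to date, not Cohort 1, and may already include laboratory terms.

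**Conclusion.** The point holds in a limited form. As written, the plan yields no per-patient incidence of the hepatic AESI defined in protocol 7.2.4, and no onset or resolution times for it. Some qualifying patients can be absent from the SAP VIII.B tables, depending on how sites apply 7.2.2. The size of the undercount cannot be derived from the documents. The conclusion rests on the text of the two documents and on no assumed rate.

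One dependency remains. The SAP says it follows protocol version 5, while the protocol supplied refers to Version 7/Amendment 6. Whether 7.2.4 read the same in version 5 cannot be checked here; the mismatch with the current protocol stands. This is an inexpensive improvement to safety reporting, and it questions no clinical rule.

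**What to change.** In SAP VIII.B, add a per-patient hepatic AESI variable that applies 7.2.4(a) to the laboratory dataset from first dose to 28 days after last dose, including unscheduled samples. State whether baseline is judged per parameter or across all liver tests. Combine the variable with reported hepatic AEs and reconcile it with the AESI Forms. Report incidence, time to onset and time to resolution beside the preferred-term tables, which can stay as they are. Confirm in the SAP that the derivation matches the current 7.2.4.

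The cost is one derived variable and one table from chemistry already collected and graded, some reconciliation work, and a hepatic AESI rate that may be less favourable. No site procedure changes.

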4.2 Phase 2 Stage

Specific populations of patients with AML/MDS harboring IDH1-R132 mutations will be enrolled to further characterize the safety and efficacy of FT-2102 at the RP2D in Phase 2 cohorts. Only 1 dose level of FT-2102 as SA and 1 dose level of FT-2102 in combination with azacitidine will be evaluated in the proposed Phase 2 cohorts.

FT-2102 150 mg BID is the RP2D (see Section 1.5.1). This RP2D has been confirmed for SA and azacitidine combination treatment.

Phase 2 cohorts may include the following:

Single-Agent Cohorts:

Cohort 1 (SA FT-2102): approximately 173 evaluable patients with R/R AML. To account for discordance between local and central mutation testing, approximately 190 patients may be enrolled into this cohort to obtain 173 evaluable patients.

Cohort 2 (SA FT-2102): approximately 53 patients with AML in morphologic CR/CRi after prior therapy (+/- HSCT) with residual IDH1-R132 mutation ($\geq 0.01\%$) detected in the bone marrow.

Cohort 3 (SA FT-2102): approximately 20 patients with R/R AML/MDS that have been previously treated with FT-2102. Patients who undergo HSCT on-study then relapse post-HSCT are allowed in this cohort.

Azacitidine Combination Cohorts:

Cohort 4 (FT-2102 in combination with azacitidine): approximately 20 patients with R/R AML/MDS that is naïve to prior hypomethylating therapy and IDH1 inhibitor therapy.

Cohort 5 (FT-2102 in combination with azacitidine): approximately 20 patients with R/R AML/MDS that have inadequately responded to or have progressed on prior hypomethylating therapy.

Cohort 6 (FT-2102 in combination with azacitidine): approximately 44 patients with R/R AML/MDS that have been previously treated with SA FT-2102 as their last therapy prior to study enrollment. The actual number of patients in this cohort may be larger, since patients from the FT-2102 SA cohorts of this study are allowed to be enrolled in Cohort 6 after their disease progression.

Treatment Naïve Cohorts:

Cohort 7 (SA FT-2102): Approximately 54 treatment naïve AML patients for whom standard treatments are contraindicated.

Cohort 8 (FT-2102 in combination with azacitidine): Approximately 28 treatment naïve AML patients who are candidates for azacitidine as a first line treatment.

Note for Phase 2 Cohort 7 and Phase 2 Cohort 8: Treatment naïve is defined as no prior treatment for AML. Patients may have received a prior treatment for another hematologic malignancy.

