5.5 Precautions

5.5.1 Differentiation Syndrome

Differentiation syndrome has been observed in patients participating in this ongoing study and has also been reported in patients with AML/MDS receiving other therapies targeting IDH1/2 mutations (Birendra et al. 2016; Fathi et al. 2018) or receiving azacitidine (Laufer and Roberts 2015).

Differentiation syndrome can be defined by the presence of any of the following symptoms: unexplained fever, cough, fast weight gain of more than 10 pounds (5 kg) within a week, bone pain, dizziness or feeling lightheaded, respiratory distress or shortness of breath, interstitial pulmonary infiltrates, pleural or pericardial effusion, swelling of arms & legs and swelling around the neck, groin or underarm with or without hyperleukocytosis (Frankel et al. 1992; Montesinos et al. 2009). No single sign or symptom may be considered per se as diagnostic of the syndrome. However, given the life-threatening character of a full-blown (overt) syndrome, it is recommended that the prophylactic and therapeutic measures indicated below are undertaken at the earliest manifestations of suspected differentiation syndrome (e.g., unexplained respiratory distress).

- Temporary discontinuation of FT-2102 (and azacitidine where indicated) for a minimum of three days;
- Prompt initiation of dexamethasone, 10 mg/12 hrs IV until disappearance of symptoms and signs, and for a minimum of three days;
- Furosemide, supportive measures and hemodynamic monitoring when clinically required.

As soon as the symptoms and the patient's clinical condition improve, and after a minimum of three days, treatment with FT-2102 may be resumed. In case of reappearance of symptoms, FT-2102 should again be held. Resumption of FT-2102, if indicated, should be reduced one dose level for a minimum of the first 7 days after the disappearance of the differentiation syndrome. Thereafter, in absence of worsening of the previous toxicity, FT-2102 can be resumed at full dosage.

Where indicated, as soon as the symptoms and the patient's clinical condition improve, and after a minimum of 3 days, treatment with azacitidine may be reinstituted at \leq standard dosing and/or delayed further at the investigator's discretion. No dose modifications are required for LDAC.

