6 STUDY PROCEDURES

6.1 Measurements and Evaluations

See Appendix 1 and Appendix 2 for a detailed study Schedule of Events, including measurements and evaluations for the entire study period (Screening to Follow-up) presented in tabular form.

For Protocol Version 7/ Amendment 6, a reduced Schedule of Events has been introduced for all ongoing patients receiving treatment at the time of the amendment (see Appendix 1) and a new Schedule of Events has been added for patients enrolled after Protocol Version 7/ Amendment 6 (eg, patients that transfer from Cohort 1 to Cohort 3 or Cohort 6) (see Appendix 2).

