9.2.4.2 Safety Analysis

For DLT-evaluable patients, the summary of DLTs will be provided by dose/dosing schedule for patients in the Phase 1 dose-escalation stage. All other safety analyses will be based on the Safety Set.

For each stage, the safety and tolerability of FT-2102 will be assessed, as evaluated by adverse events, concomitant medication usage, changes from baseline in physical examination, vital signs, clinical laboratory evaluations, and ECG. Safety data will be listed by patient and summarized descriptively.

A treatment-emergent adverse event (TEAE) is defined as an adverse event with onset on or after the start of study drug, or any worsening of a pre-existing medical condition/adverse event with onset on or after the start of study drug and until 28 days after the last dose. For each stage, all adverse events will be coded using MedDRA version 19.1 or higher and summarized by SOC and PT, for each treatment group. Multiple occurrences of an AE are counted only once per patient per SOC and PT for summary tables. Causality of TEAEs (not related, related) and severity (NCI CTCAE version 4.03 or higher) will be summarized by treatment for each stage.

Relationship will be presented by study drug when applicable. All adverse events and serious adverse events (including those with onset or worsening before the start of study drug) will be listed.

Safety laboratory, vital sign, ECG and physical examinations will be summarized by visit. The change from baseline will be presented along with the by-visit summaries. Shifts in laboratory grades, as well as QTcF shifts, will be tabulated. Assessment of changes in liver function tests will be conducted. Abnormal safety assessments will be flagged and separately presented. All safety data will be listed.

Assessment of differentiation syndrome will be conducted as per Montesinos et al. 2009, searching for candidate cases of differentiation syndrome based on AE reports of dyspnea, pulmonary infiltrates, edema, weight gain, pleural effusion, renal failure, hypotension, pericardial effusion, and unexplained fever. Specific methods of identifying candidate cases will be fully described in the Statistical Analysis Plan (SAP).

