Differentiation syndrome (DS) is a risk of drugs in this class. While many of the symptoms of differentiation syndrome are non-specific and best judged by the treating clinician, in the spirit of the article by Montesinos et al. (2009), and using methodology outlined by Norsworthy et al. (2020), candidate cases of DS will be summarized. This analysis will be conducted for IA2 only, and not for the final study reporting.

The number of patients with an investigator reported AE of DS will be summarized.

In addition, candidate cases of DS will be summarized based on AE data and also leukocyte count results from the laboratory data set. AE preferred terms will be summarized into categories representing possible symptoms of DS as per the table below, and tabulated by the number of patients experiencing an AE in the category in the first 90 days and 180 days post first dose.

Candidate DS AESI Symptom Category	AE Preferred Terms
Dyspnoea	Acute respiratory distress syndrome Acute respiratory failure Cardiopulmonary failure Cardio-respiratory distress Cough Dyspnoea Dyspnoea exertional Dyspnoea at rest Orthopnea Productive cough Respiratory distress

Pulmonary infiltrates or	Acute interstitial pneumonitis
Pleuropericardial effusion	Acute lung injury
1	Acute pulmonary oedema
	Acute respiratory distress syndrome
	Atypical pneumonia
	Bilateral pulmonary infiltrates
	Generalized oedema
	Interstitial pneumonitis
	Localized oedema
	Lower respiratory tract infection
	Lower respiratory tract inflammation
	Lung infiltration
	Non-cardiogenic pulmonary oedema
	Pericardial effusion
	Preumania
	Pneumonitis
	Pneumonitis
	Pulmonary infiltration NOS
	Pulmonary congestion
	Pulmonary congestion
	Pulmonary toxicity
	Tumonary toxicity
Kidney injury	
	Acute kidney injury
	Anuria
	Blood creatinine abnormal
	Blood creatinine increased
	Cardiorenal syndrome
	Hepatorenal failure
	Prerenal failure
	Renal failure
	Renal failure acute
	Renal function test abnormal
	Renal impairment
	Renal injury
TT / '	Creatinine value >26.52 μ mol/L or >1.5x baseline value in the lab dataset
Hypotension	Hypotension
	Orthostatic hypotension
	Blood pressure decreased
	Blood pressure systolic low
	Blood pressure diastolic decreased
	Any systolic blood pressure in vital signs data set < 90 mmHg
Fever	Pyrexia
	Febrile bone marrow aplasia
	Febrile neutropenia
	Temperature in vital signs data set $> 38.3^{\circ}$ C
Weight gain	Capillary leak syndrome
-0 0	Fluid overload

Fluid retention
Generalized oedema

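### The creatinine trigger in the SAP's differentiation-syndrome search is set at 0.30 mg/dL as an absolute value, so nearly every patient exceeds it; the search is also not repeated after IA2

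*SAP*

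**What the plan says.** SAP VIII.B, under the heading for DS as an adverse event of special interest, lists six symptom categories: dyspnoea, pulmonary infiltrates or effusion, kidney injury, hypotension, fever and weight gain. Most entries are adverse event terms, but some categories also have a laboratory or vital-sign trigger. For kidney injury that trigger begins "Creatinine value >26.52" μmol/L and offers more than 1.5 times the baseline value as the alternative. The weight trigger states explicitly that it is a change from baseline. The first creatinine limb does not.

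A patient becomes a candidate with at least two categories that start within 7 days of each other. A committee then adjudicates candidates. For adjudicated cases without an investigator-reported DS event, severity is a count: two or three concurrent categories is moderate, more than three is severe.

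On timing, the SAP says of the candidate-case summary: "This analysis will be conducted for IA2 only, and not for the final study reporting". Protocol 9.2.4.2 commits to a search of adverse event reports for candidate cases and ties it to no particular analysis. It delegates the methods: "Specific methods of identifying candidate cases will be fully described in the Statistical Analysis Plan (SAP". Apart from the dose-limiting toxicity summary, it adds: "All other safety analyses will be based on the Safety Set".

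**The concern.** The search exists to find DS that the investigator did not record as DS. Protocol 5.5.1 explains why this matters: it warns that no single sign is diagnostic and asks for early action "given the life-threatening character of a full-blown (overt) syndrome". A search that needs two categories works only if each category separates affected from unaffected patients. A kidney trigger that is met at normal creatinine reduces the two-category rule towards a one-category rule. It can also add one to the severity count.

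The second issue is coverage. Treatment continues after IA2, and protocol 6.1 foresees "patients that transfer from Cohort 1 to Cohort 3 or Cohort 6" after Amendment 6. Uncoded DS arising in that later exposure is never put through the combination rule.

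**Working it through.** **1. The trigger in clinical units.** Using the standard conversion of 88.4 μmol/L per mg/dL, 26.52 / 88.4 = 0.30 mg/dL.

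**2. Comparison with the SAP's own definition of normal.** SAP VI.J gives clearance = (140 − age) × weight × (0.85 if female) / (72 × creatinine in mg/dL) and calls 90 mL/min or more normal. The three patients below are assumed examples.

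| Example patient | Clearance at 0.30 mg/dL | Creatinine at 90 mL/min | Multiple of 26.52 |
|---|---|---|---|
| Man, 65 y, 75 kg | 75 × 75 / 21.6 = 260 | 5625 / 6480 = 0.868 mg/dL = 76.7 μmol/L | 2.89 |
| Woman, 75 y, 60 kg | 65 × 60 × 0.85 / 21.6 = 153 | 3315 / 6480 = 0.512 mg/dL = 45.2 μmol/L | 1.71 |
| Woman, 85 y, 45 kg | 55 × 45 × 0.85 / 21.6 = 97 | 2103.75 / 6480 = 0.325 mg/dL = 28.7 μmol/L | 1.08 |

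(72 × 0.30 = 21.6 and 72 × 90 = 6480.) All three exceed the trigger with normal function and no change from baseline. Lower clearance gives higher creatinine, so impaired patients exceed it by more.

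**3. What the wording does to the other limb.** If the first limb is absolute, the 1.5-times limb adds something only when baseline is below 26.52 / 1.5 = 17.68 μmol/L (0.20 mg/dL), so it is practically idle. If the first limb is a rise, both limbs work: 1.5 × baseline exceeds baseline + 26.52 only when baseline is above 26.52 / 0.5 = 53.04 μmol/L. The rise then gives the lower threshold for higher baselines and the ratio gives it for lower ones. With the creatinine values above as baselines, the corrected thresholds are about 103, 68 and 43 μmol/L.

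**4. Consequence for the 7-day rule.** The SAP defines concurrence by adverse event start dates and does not say what the start date of a laboratory trigger is. There are two readings.

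- *Every qualifying sample is an onset.* Scheduled chemistries in protocol Appendix 1 fall on study days 1, 5, 8, 12, 15, 19, 22, 26, 29, 36, 43, 50, 57, 71 and 85. Every day from 1 to 92 is within 7 days of one. SAP Appendix 1 has no Cycle 3 Day 15 sample, so its unbroken run ends at Day 57 + 7 = 64. Any one other category with onset in that span then makes a candidate, and three others become four, which is severe.
- *Only the first qualifying sample is an onset.* This falls on Day 1, or on Day 5 if the Day 1 sample is baseline. It pairs only with events up to Day 8 or Day 12, so the over-flagging is confined to the start of treatment.

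**5. Coverage after IA2.** The protocol commits to the search and delegates how cases are identified. The SAP confines the search to IA2, and no other section restores it. The documents do not give the exposure after the cut. For Cohort 1, planned enrolment of about 190 less the 115 patients in the IA2 efficacy evaluable set leaves up to 75. That set excludes patients first dosed less than 180 days before the cut and those without central confirmation, who may nonetheless be in the Safety Set. The number first dosed after the cut is therefore anywhere from 0 to about 75. Roll-overs and continuing patients add exposure of unknown size.

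**6. Limit on a later search.** Under protocol Appendix 2, scheduled chemistry falls on days 1, 57, 113 and 169. The days within 7 of a sample are 8 + 15 = 23 of the first 90 (26%) and 8 + 15 + 15 + 15 = 53 of 180 (29%). Laboratory triggers will therefore be less sensitive in patients enrolled after Amendment 6. Steps 4 and 6 assume nominal visit days and no unscheduled samples.

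**The case against.** On the trigger, the best reply is that the intent is obvious. The figure equals 0.3 mg/dL and sits beside a ratio to baseline, so a programmer would probably supply the missing reference to an increase. Adjudication would also remove false candidates, leaving mainly extra review work. Both points have force, and step 4 shows that the severity effect depends on an onset rule the SAP does not state. But the SAP is the specification, the weight trigger shows how a change from baseline is written there, and adjudication does not reset the category count that grades severity.

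On timing, the limit is deliberate: the SAP's summary of changes says that some IA2 analyses will not be repeated. The protocol is silent on which analysis carries the search. Patients in the IA2 efficacy evaluable set were at least 180 days from first dose, so their 90- and 180-day windows had closed. DS also does not vanish from the final report. Investigator-coded DS and its component events still reach the standard tables, the special-interest table by organ class and preferred term has no IA2 limit, and "All AEs occurring on study (treatment emergent or not) will be provided in patient data listings". Medical-monitor and internal committee review continues under protocol 6.2.1. All of this stands and makes the timing point secondary. It does not supply the combination search, and the protocol delegated methods, not the decision to leave later data unsearched.

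**Conclusion.** The creatinine trigger is wrong as written and should be corrected for IA2 and for any later use. As an absolute value it is met at normal renal function in all three examples, by factors of 1.08 to 2.89, so the laboratory limb carries almost no information. How far this inflates candidates depends on the onset rule: from the first 8 to 12 days up to 64 or 92 days without a gap under the pre-Amendment 6 schedules. The shift from moderate to severe requires that each sample counts as an onset, and it applies only to adjudicated cases with no investigator-reported DS event.

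The IA2-only limit is a lesser gap of unknown and possibly small size.

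A reader might infer more than the documents support:

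- That the IA2 results are wrong. The documents do not show how the trigger was programmed.
- That DS goes unreported at the end. Coded DS and component events remain.
- That patients rolling into Cohort 6 are all new to azacitidine. Azacitidine is new for them on study if they come from a single-agent cohort, but Cohorts 1 and 6 do not bar prior hypomethylating therapy, so there is no firm basis for restarting their windows at Cohort 6 entry.

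**What to change.** 1. In the SAP VIII.B table, change the trigger to: creatinine increase of more than 26.52 μmol/L (0.3 mg/dL) from baseline, or more than 1.5 times baseline. Add that onset is the date of the first qualifying sample of an episode.
2. Check whether the IA2 candidate and severity outputs used the literal value. If they did, rerun them.
3. At the final analysis, rerun the candidate program with the corrected trigger on the Safety Set by cohort. Show candidates after the IA2 cut in a separate row labelled as candidates, not adjudicated. At minimum, state in the study report that adjudicated DS incidence is as of the IA2 cut, and why.

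The cost is one corrected line, one onset rule, a programming check and a rerun on data already collected. The committee need not be reconvened for post-IA2 candidates. The drawback is interpretive: unadjudicated candidates are non-specific, since cough and febrile neutropenia count, and laboratory and vital-sign triggers are sparser under protocol Appendix 2. The later counts are not comparable with the adjudicated IA2 figures and should not replace them.
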